6.5. Randomization and Masking

A stratified permuted-block randomization will be employed to randomize eligible subjects in a 1:1 ratio to either DE-126/Vehicle arm or Timolol Maleate arm. The randomization will be stratified by mean diurnal IOP in the study eye at baseline visit (Visit 2): <25 mmHg vs. \geq 25 mmHg.

The randomization schedule will be generated and implemented using central randomization via Interactive Response Technology (Medidata Rave RTSM). Each randomized subject will receive numbered study medication kits as assigned by Medidata Rave RTSM.

This is a double-masked study. The subjects, Investigators, Examiners, and Santen personnel involved in the conduct of the study will be masked to the study treatment. An authorized unmasked study staff member at the investigative site who is not the Investigator or Examiner will dispense and collect study medication(s) and will query about dosing compliance.

Subjects will be instructed not to show the eye drop bottles or discuss the eye drop to either the Investigator or the Examiner or other study subjects. The active control treatment (Timolol Maleate) containers will be over-labeled and packaged in the same secondary package (e.g., cardboard kit carton) as the investigational treatment (DE-126). Subjects on DE-126/Vehicle arm will receive a kit containing 2 bottles labeled "morning" for the morning dose and 2 bottles labeled "evening" for the evening dose. Subjects on Timolol arm will receive a kit containing 2 bottles labeled morning/evening for the BID dosing.

Each eligible subject will receive a numbered study medication kit assigned by Central randomization via Interactive Response Technology (Medidata Rave RTSM) at Visit 2 (Baseline, Day 1) and at Visit 4 (Week 6).

In case of a medical emergency, the Principal Investigator may reveal the treatment information by unmasking through Medidata Rave RTSM to know which treatment the subject has received. The Principal Investigator (or his/her designee) should contact Santen, or Santen's designee, before taking this measure, if there is sufficient time. Santen, or Santen's designee, must be informed of all instances where the code is broken and of the reasons for such instances.

Additionally, the AE or SAE for which study treatment was unmasked should be reported to Santen Pharmacovigilance.

7. DISCONTINUATION OF INVESTIGATIONAL PRODUCT AND SUBJECT DISCONTINUATION/WITHDRAWAL FROM STUDY

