9.7.2.2. Other Secondary Efficacy Endpoints

Other secondary endpoints to be assessed include:

- Mean diurnal IOP in the study eye at Week 2 (Visit 3) and Week 6 (Visit 4)
- Change and percent change from Baseline (Visit 2, Day 1) in IOP in the study eye at each timepoint of each post-baseline visit
- Change and percent change from Baseline (Visit 2, Day 1) in mean diurnal IOP in the study eye at each post-baseline visit
- Having a mean diurnal IOP reduction $\geq 20\%$, $\geq 25\%$, or $\geq 30\%$ from Baseline (Visit 2, Day 1) in the study eye at each post-baseline visit

- Having a mean diurnal IOP \leq 18mmHg in the study eye at each post-baseline visit

The continuous secondary endpoints will be analyzed using MMRM on observed cases. More details on the model specifications will be provided in the SAP.

The binary secondary endpoints will be analyzed using the Pearson's chi-square test for a 2x2 contingency table. The Fisher's Exact test may be conducted as a sensitivity analysis.

Subgroup analyses by the two randomization strata (baseline IOP in the study eye <25 mmHg vs. ≥ 25 mmHg) be performed for secondary endpoints using descriptive statistics.

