1. INTRODUCTION

This statistical analysis plan (SAP) specifies the statistical methods to be implemented for the analysis of data collected from the 012604IN study within the scope of Santen's Protocol 012604IN, "A Phase IIb, Randomized, Double-Masked, Active-Controlled, Parallel-Group, Multicenter Study Assessing the Efficacy and Safety of DE-126 Ophthalmic Solution 0.002% Compared with Timolol Maleate Ophthalmic Solution 0.5% in Subjects with Primary Open Angle Glaucoma (POAG) or Ocular Hypertension (OHT)". It applies to the Study Protocol Amendment 1 dated 18 February 2021 and provides detailed instructions as to how each analysis will be performed.

Results obtained from the analyses specified in the final approved version of the SAP will become the basis of the clinical study report (CSR) for this study. Any deviations from the final approved version of the SAP must be substantiated by sound statistical reasoning and documented in the CSR.

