6.1. Adjustments for Covariates

In general, baseline IOP score will be adjusted in the inferential analysis of each IOP endpoint. Detailed information on covariate adjustment is provided in Section 8.1.

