6.4. Multiple Comparisons / Multiplicity

Fixed sequence procedure will be applied to control the overall Type I error rate across the four hypotheses in the primary and key secondary endpoints at the 0.05 level. Fixed sequence procedure tests hierarchically ordered hypotheses at level 0.05 until the first non-rejection.

The fixed sequence for the four hypotheses in this study is as follows:

1. Hypothesis of non-inferiority of DE-126 ophthalmic solution 0.002% to Timolol maleate ophthalmic solution 0.5% for the primary endpoint, IOP at each scheduled timepoint (08:00, 10:00, and 16:00) at Week 2, Week 6, and Month 3.
2. Hypothesis of non-inferiority of DE-126 ophthalmic solution 0.002% to Timolol maleate ophthalmic solution 0.5% for the key secondary endpoint, mean diurnal IOP at Month 3.
3. Hypothesis of superiority of DE-126 ophthalmic solution 0.002% to Timolol maleate ophthalmic solution 0.5% for the key secondary endpoint, mean diurnal IOP at Month 3.
4. Hypothesis of superiority of DE-126 ophthalmic solution 0.002% to Timolol maleate ophthalmic solution 0.5% for the primary endpoint, IOP at each scheduled timepoint (08:00, 10:00, and 16:00) at Week 2, Week 6, and Month 3.

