8.2.1. Responder Rates

For binary secondary endpoints, the responder rates will be summarized at each post-baseline visit. Subjects discontinued study by any reason without response will be treated as non-responder. A sensitivity analysis will be conducted by multiple imputing for discontinued subjects with reasons other than AE or lack of efficacy. DE-126/Vehicle arm will be compared with Timolol Maleate arm using Fisher's exact test, and the differences between the two treatment arms will be reported along with 95% CIs.

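### SAP 8.2.1 makes Fisher's exact test the only test of the responder endpoints where the protocol names Pearson's chi-square; neither uses the randomisation stratum, and the confidence interval has no named method

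*SAP*

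**What the plan says.** Protocol 9.7.2.2: "The binary secondary endpoints will be analyzed using the Pearson's chi-square test for a 2x2 contingency table". On the alternative test it adds: "The Fisher's Exact test may be conducted as a sensitivity analysis".

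SAP 8.2.1 names one test only: "DE-126/Vehicle arm will be compared with Timolol Maleate arm using Fisher's exact test". It continues that "the differences between the two treatment arms will be reported along with 95% CIs", without naming an interval method. Pearson's test does not appear in the available SAP text. SAP Section 1 ties the SAP to Protocol Amendment 1, the version that names Pearson, and says that results from the SAP's analyses "will become the basis of the clinical study report (CSR) for this study".

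On the stratum, protocol 6.5 says: "The randomization will be stratified by mean diurnal IOP in the study eye at baseline visit (Visit 2"), with the cut at <25 versus ≥25 mmHg; SAP 3.2 repeats this. SAP 6.1 says: "In general, baseline IOP score will be adjusted in the inferential analysis of each IOP endpoint". For the responder endpoints, the strata appear only in descriptive subgroup summaries (protocol 9.7.2.2, SAP 8.3).

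The fixed sequence in SAP 6.4 controls error "across the four hypotheses in the primary and key secondary endpoints"; the responder endpoints are not among them.

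**The concern.** The SAP promotes the protocol's optional test to sole test and drops the protocol's main one. The SAP governs the report, so Fisher's test is what will be reported, and after unmasking someone may fairly ask which test was pre-specified.

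Three things are at stake:

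- Fisher's test gives up some power at this sample size.
- The stratum is randomised on and recorded, yet neither test uses it.
- With no interval method named, the p-value and CI in the same table can point in different directions.

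**Working it through.** The documents give no responder rates and no power for these endpoints, so there is no stated figure to reproduce.

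**1. Size and power of the two unstratified tests.** Inputs: 140 evaluable per arm (protocol 9.3.1, SAP 3.3), 1:1 allocation, two-sided 0.05 (SAP 6). The response rates are assumptions. For each test, the rejection probability is

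Σₓ Σᵧ Bin(x; 140, p₁) · Bin(y; 140, p₀) · 1{p-value ≤ 0.05},

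summed over all 141 × 141 = 19,881 tables. Pearson is without continuity correction.

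| True rates | Fisher | Pearson | Difference |
|---|---|---|---|
| 50% vs 50% | 3.63% | 4.84% | 1.21 |
| 55% vs 45% | 33.78% | 38.28% | 4.50 |
| 57.5% vs 42.5% | 66.48% | 70.75% | 4.27 |

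Fisher never rejects a table that Pearson does not, while 264 tables are significant by Pearson only. The last column is therefore also the chance that the two disagree. To one decimal, it is also the chance that Fisher gives p > 0.05 while a Wald or Newcombe CI excludes zero.

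Over common null rates of 30% to 70%, size is 3.6% to 3.7% for Fisher and 4.8% to 5.1% for Pearson. For a 15-point difference over control rates of 30% to 70%, power is 67% to 83% for Fisher and 71% to 86% for Pearson. At a 10-point difference the loss reaches about 5 points.

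**2. One table.** Take 79/140 against 62/140 responders.

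- Difference: 17/140 = 12.1 points. Pooled rate: 141/280 = 0.5036.
- Pearson: z = 0.1214 / √(0.5036 × 0.4964 × 2/140) = 0.1214 / 0.0598 = 2.03, p = 0.042.
- Fisher: p = 0.056.
- Wald CI: 0.1214 ± 1.96 × √(0.5643 × 0.4357/140 + 0.4429 × 0.5571/140) = 0.1214 ± 0.1163, that is 0.5 to 23.8 points. Newcombe gives 0.4 to 23.4.

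The band is narrow: against 62/140, Pearson is significant from 79 responders and Fisher from 80.

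**3. Value of the stratum.** This was simulated with 20,000 trials per setting, 140 per arm, in blocks of 4 within stratum. All distributional inputs are assumed: baseline = min(22 + Gamma(shape 2, scale 1.75), 34); on-treatment mean diurnal IOP = 18.5 − 1.0 × arm + slope × (baseline − 25.5) + N(0, SD 3). CMH is without continuity correction. Monte Carlo error is about 0.35 points for power.

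| Slope, endpoint ≤18 mmHg | Fisher | Pearson | CMH | CMH − Pearson |
|---|---|---|---|---|
| 0.4 | 52.2% | 56.1% | 57.5% | 1.4 |
| 0.6 | 47.2% | 51.2% | 55.0% | 3.8 |
| 0.8 | 41.6% | 45.8% | 51.5% | 5.7 |

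For the three percent-reduction endpoints, CMH minus Pearson runs from −0.1 to +1.0 points. Null rejection across all four endpoints is 4.6% to 5.3% for CMH, 3.7% to 5.2% for Pearson and 2.8% to 4.2% for Fisher.

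A second simulation used two equal strata, a 45% control rate and a 15-point difference. CMH/Pearson/Fisher power was 71/71/67% with no gap in response between strata, 73/71/67% with a 20-point gap and 79/73/68% with a 40-point gap. The gain from stratifying depends on how strongly the stratum predicts response.

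**The case against.** **The sponsor may choose a conservative test.** Four endpoints at three visits give 12 nominal comparisons without multiplicity control, and a valid, mildly conservative test is defensible there. Pearson is not exactly at its nominal level either: at 147 per arm and 50% response its size is 5.4%, against 4.1% for Fisher. The planning assumption is a difference of 0 mmHg, under which there is no power to lose. All of this stands, and it keeps the point minor. It does not reconcile the two documents or supply a CI method.

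**A reader might infer an undisclosed change.** The documents do not support that. Some SAP front matter was not available, so a revision note cannot be ruled out. Protocol Section 9 also leaves detailed methods to the SAP. All that can be said is that no record or reason appears in the available text.

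**A reader might infer that the SAP breaks its own covariate rule.** SAP 6.1 is hedged, speaks of the baseline IOP score rather than the stratum, and points to Section 8.1, which covers only the repeated-measures models. Those models adjust for baseline IOP and do not include the stratum either. On stratification the protocol and SAP agree with each other, so using the stratum is an improvement and not the repair of a contradiction.

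**CMH is named in neither document**, and its gain is confined to the ≤18 mmHg endpoint under an assumed slope. That is correct. Effect, treated mean and residual SD were also held at single values in the power runs.

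**A reader might infer that subjects still on study with a missing time point drop out of the denominator.** SAP 4.2.4, read with the full analysis set in SAP 8, most naturally keeps them in. This is at most a point to clarify.

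**Conclusion.** The mismatch between protocol 9.7.2.2 and SAP 8.2.1 is plain, and the missing CI method is a real gap. A reader might take the switch for a validity error; it is not. Fisher's test controls type I error, and the cost is about 4 points of power against Pearson at 140 per arm with response near 50%, which is an assumed rate.

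Stratifying adds roughly 1 to 6 points over Pearson for ≤18 mmHg, assuming a 1.0 mmHg effect, residual SD 3 and baseline slope 0.4 to 0.8. It adds about nothing for the percent-reduction endpoints. No confirmatory conclusion changes. The point is worth fixing because it is minor and nearly free to fix.

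**What to change.** Before unmasking, in SAP 8.2.1:

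1. Reconcile the section with protocol 9.7.2.2, state which test is the main one, and record the change and the reason.
2. Preferably, make the main test CMH without continuity correction, stratified by baseline mean diurnal IOP <25 versus ≥25 mmHg. Report the Mantel-Haenszel risk difference with its 95% CI, and keep Pearson and Fisher as sensitivity analyses. Test and estimate then share the same stratum weights. Borderline disagreement can still occur, because the CMH variance is computed under the null.
3. At minimum, restore the protocol's Pearson test and name a CI that matches it. A Wald interval does not fully match: at 30% versus 20% with 140 per arm, it excludes zero while Pearson gives p > 0.05 in 0.75% of trials; Newcombe gave none there. This option recovers the loss for the percent-reduction endpoints, but only part of the Fisher-to-CMH gap for ≤18 mmHg: 74%, 51% and 42% at slopes 0.4, 0.6 and 0.8.

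Optionally, add a sentence on how subjects still on study without a calculable mean diurnal IOP are counted. Imputing them would extend the multiple imputation in SAP 8.2.1, which covers only subjects who discontinued for reasons other than AE or lack of efficacy.

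The cost is SAP wording and a few lines of code. The stratum is already recorded.

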8.3. Subgroup Analyses

To assess the homogeneity of treatment effects among subgroups, descriptive summaries for all IOP endpoints will be conducted by the following categories:

- age group (< 65, or \geq 65 years)
- sex (males or females)

- race (White or non-White)
- mean diurnal IOP in the study eye at baseline visit (<25 mmHg vs. \geq 25 mmHg)
- primary ocular diagnosis (primary open-angle glaucoma or ocular hypertension).

If there are a sufficient number of subjects in each subgroup, the test of interaction will be conducted using an MMRM with treatment, visit, treatment-by-visit, subgroup, and treatment-by-subgroup as fixed effects, baseline IOP score (score at the corresponding timepoint or mean diurnal score) as a covariate, and subject as a random effect.

9. SAFETY ANALYSES

The safety-related measures collected in this study include AEs, slit-lamp biomicroscopy, ophthalmoscopy, corrected visual acuity, ocular symptoms, central corneal thickness, iris color, eyelash, and eyelid by photographs, vital signs, and clinical laboratory tests. The Safety population will be used for all safety summaries, where subjects will be classified by actual treatment received. If a subject was administered a different treatment than that which was assigned in the study, this subject will be included in the higher dose of DE-126 arm or Timolol arm if the subject didn't receive any DE-126 in the study.

All the safety-related measures will be summarized descriptively by actual treatment received. Except AEs, the descriptive summary of each safety-related measure and the change from baseline in that measure will be performed.

9.1. Adverse Event

Subjects with any AEs will be tabulated AEs by treatment arm using actual treatment received. Subjects with any AEs will be tabulated by SOC and PT where a subject who experienced multiple AEs within a SOC or PT will be counted only once for that SOC or PT. SAEs, SARs, and Serious SARs will be tabulated similarly.

Subjects with any ocular and non-ocular AEs will be tabulated separately. AEs, ocular, and non-ocular will also be summarized by relationship to treatment and maximum severity. Any ocular AE that occurred simultaneously to both eyes will be counted once.

AE, SARs, ocular and non-ocular AEs will also be summarized by country.

AEs, AEs leading to death, AEs leading to discontinuation, SAEs, and ESIs, if any, will be listed separately.

9.2. Best-Corrected Visual Acuity

BCVA measures the acuteness or clearness of the best-corrected vision, with a range of [0, 97] in ETDRS letters. An increase in BCVA indicates an improvement in the best-corrected vision.

BCVA will be measured for each eye prior to the 08:00 IOP measurement at each visit at Baseline, Week 2, Week 6, and Month 3 using a Snellen chart using visual acuity chart (Early Treatment Diabetic Retinopathy Study [ETDRS] chart) and the logMAR scoring.

BCVA in Snellen scale will be converted to logMAR scale using the following equation and be used in all the BCVA analyses:

$$\text{LogMAR VA} = -\log_{10} \left(\frac{\text{Snellen numerator}}{\text{Snellen denominator}} \right)$$

BCVA (logMAR scores) and changes from baseline will be summarized by treatment and analysis visit for study eyes and fellow eyes, separately. In addition, any change (worsening or improvement) of ≥ 0.2 LogMAR (2 lines) from baseline will be summarized and listed.

9.3. Slit-lamp Biomicroscopy

For each biomicroscopy parameter, frequency and percentage of severity rating score will be summarized by actual treatment received and analysis visit for study eyes and fellow eyes, separately. In addition, subjects with improvement (decrease) or worsening (increase) or maintaining from baseline in severity rating score will be tabulated by analysis visit and biomicroscopy parameter. Subjects with worsening of 2 units or more from baseline will be listed.

9.4. Ophthalmoscopy

For cup to disc ratio, scores and changes from baseline will be summarized by actual treatment received and analysis visit for study eyes and fellow eyes, separately.

For glaucomatous optic nerve, frequency and percentage of severity rating score will be summarized by actual treatment received and analysis visit for study eyes and fellow eyes, separately.

9.5. Central Corneal Thickness

Central corneal thickness scores at screening will be summarized by actual treatment received for study eyes and fellow eyes, separately.

9.6. Vital Signs

Blood pressures and pulse rate, and changes from baseline may be summarized by actual treatment received and analysis visit.

10. ANALYSIS OF EXPLORATORY ENDPOINT

Glaucoma Quality of Life-15 (GQL-15) questionnaire (protocol Appendix F) is a 15-item questionnaire measuring the severity of visual disability in glaucoma patients. The GQL-15 will be administered at Baseline (Visit 2, Day 1) and Month 3 (Visit 5).

The GQL-15 total score and 4 domain scores will be summarized descriptively by actual treatment received. In addition, change from baseline will be presented. The 4 domains are central and near vision, outdoor mobility, peripheral vision, and dark adaption and glare.

Table 5 GQL-15 Questionnaire Items Associated with 4 Domains

Domain	Questionnaire Item
Central and near vision	1. Reading newspapers 15. Recognizing faces
Peripheral vision	4. Walking on uneven ground 8. Tripping over objects 9. Seeing objects coming from the side 11. Walking on steps/stairs 12. Bumping into objects 13. Judging distance of foot to step/curb
Glare and dark adaption	2. Walking after dark 3. Seeing at night 5. Adjusting to bright lights 6. Adjusting to dim lights 7. Going from light to dark or vice versa 14. Finding dropped objects
Outdoor mobility	10. Crossing the road

Total score is derived by summing all item-level response scores. Subscale scores are derived by coding the item-level responses on a numerical interval scale ranging from 0 (no difficulty) to 100 (severe difficulty). Subscale scores are average of the sum of scores generated for the item-level subscale responses. Higher subscale scores indicate lower QOL and greater difficulty with subscale specific tasks (Nelson et al, 2003; Sencanic et al, 2018).

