12.6. Appendix F – The Glaucoma Quality of Life-15 Questionnaire

The Glaucoma Quality of Life-15 Questionnaire

List of daily activities with the strongest relationship with visual field loss in glaucoma

Patient instruction: Please, circle the correct answer on the scale ranging from 1 to 5 where [1] stands for no difficulty, [2] for a little bit of difficulty, [3] for some difficulty, [4] for quite a bit of difficulty, and [5] for severe difficulty. If you do not perform any of the activities for other than visual reasons please circle [0].

Does your vision give you any difficulty, even with glasses, with the following activities?

	None	A little bit	Some	Quite a lot	Severe	Do not perform for non-visual reasons
Reading newspapers	1	2	3	4	5	0
Walking after dark	1	2	3	4	5	0
Seeing at night	1	2	3	4	5	0
Walking on uneven ground	1	2	3	4	5	0
Adjusting to bright lights	1	2	3	4	5	0
Adjusting to dim lights	1	2	3	4	5	0
Going from light to dark room or vice versa	1	2	3	4	5	0
Tripping over objects	1	2	3	4	5	0
Seeing objects coming from the side	1	2	3	4	5	0
Crossing the road	1	2	3	4	5	0
Walking on steps / stairs	1	2	3	4	5	0
Bumping into objects	1	2	3	4	5	0
Judging distance of foot to step / curb	1	2	3	4	5	0
Finding dropped objects	1	2	3	4	5	0
Recognizing faces	1	2	3	4	5	0

© 1999 Patricia Nelson

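### The GQL-15 total sums code 0, a not-applicable answer, so each activity not performed counts as one point better than no difficulty

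*SAP*

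**What the plan says.** Protocol Appendix F (section 12.6) reproduces the questionnaire. The subject is told to "circle the correct answer on the scale ranging from 1 to 5 where [1] stands for no difficulty", with 5 for severe difficulty. A sixth column carries the code 0, with the instruction "If you do not perform any of the activities for other than visual reasons please circle [0". Zero is therefore not a point on the difficulty scale.

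SAP section 10, which refers to that appendix, gives the scoring:

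- Total: "Total score is derived by summing all item-level response scores".
- Domains: "coding the item-level responses on a numerical interval scale ranging from 0 (no difficulty) to 100 (severe difficulty", then averaged within the domain.
- Direction: "Higher subscale scores indicate lower QOL and greater difficulty with subscale specific tasks". For the total, the same direction follows from the 1-to-5 item codes.
- Use: "The GQL-15 total score and 4 domain scores will be summarized descriptively by actual treatment received", plus change from baseline.

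No other section deals with code 0. Protocol 8.5.3 and 9.9 give no scoring rule. SAP 6.2 covers IOP, safety measures and dates only. Protocol 9.5 bases descriptive summaries on observed cases, but a circled 0 is an observed answer, so that rule does not remove it.

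**The concern.** On a scale where lower is better and the best valid answer is 1, adding a 0 rewards the subject for an answer that carries no information about vision. The total can then fall below the best score that the difficulty scale allows. A subject who gives up an activity between baseline and Month 3 for a non-visual reason is recorded as improved. The GQL-15 is the only instrument for the exploratory objective, and both its total and its change from baseline are planned outputs. At stake is whether those tables mean what their labels say.

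**Working it through.** The documents state no range or worked example for the total, so there is no figure of theirs to reproduce. The check is arithmetic on the Appendix F codes under the SAP rule.

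**Inputs.** There are 15 items (SAP section 10; by domain 2 + 6 + 6 + 1 = 15). Difficulty codes are 1 to 5 and the not-performed code is 0 (Appendix F). The total T is the sum of the 15 codes (SAP section 10).

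**Valid range.** No difficulty on every item gives 15 × 1 = 15. Severe difficulty on every item gives 15 × 5 = 75. The span is 60 points.

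**Zeros with no difficulty elsewhere.** T = (15 − k) × 1 + k × 0 = 15 − k. For k = 1, 3 and 5 the total is 14, 12 and 10. With all 15 items coded 0 it is 0.

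**Zeros with a little difficulty elsewhere (code 2).** T = 2 × (15 − k). For k = 1, 3, 5, 7 and 8 the total is 28, 24, 20, 16 and 14. It drops below 15 only at k = 8.

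**Shortfall against a prorated total.** If the answered items average m, the SAP total is (15 − k) × m and the prorated total is 15 × m, so the shortfall is k × m. The documents give neither k nor m. The values below are assumptions chosen to show a range.

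| k zeros | mean m of the rest | SAP total | prorated | shortfall |
|---|---|---|---|---|
| 1 | 1 | 14 | 15 | 1 |
| 1 | 3 | 42 | 45 | 3 |
| 3 | 2 | 24 | 30 | 6 |
| 5 | 3 | 30 | 45 | 15 |

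The last row is 15/60 = 25% of the span.

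**Change from baseline.** An item coded b at baseline and 0 at Month 3 contributes 0 − b, that is −1 to −5, an apparent improvement. The reverse move contributes +1 to +5. An item coded 0 at both visits contributes nothing to the change.

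**Domains.** The SAP fixes the ends of the scale but gives no formula.

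- The linear map (x − 1) × 25 sends 1–5 to 0, 25, 50, 75, 100, but sends code 0 to −25, outside the stated range.
- The map x × 20 keeps code 0 at 0 but puts no difficulty at 20, against the SAP's own anchor.
- Mapping 1–5 linearly and leaving code 0 at 0 makes it identical to no difficulty.

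The SAP selects none of these. Outdoor mobility has a single item, so the treatment of a 0 there settles the whole domain score.

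**After treating 0 as missing and prorating.** With k zeros (k < 15) and no difficulty elsewhere, the total is 15 × (15 − k)/(15 − k) = 15 for every k. Three zeros and twelve items at 2 give 15 × 24/12 = 30 instead of 24. With all items coded 0 the total is missing.

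**What proration does not remove.** With all 15 items at 3, the baseline total is 45. If one item then becomes 0, the SAP total is 42 (change −3) and the prorated total is 45 (change 0). With one item at 5 and fourteen at 1, the baseline total is 19. If the 5 becomes 0, the SAP total is 14 (change −5) and the prorated total is 15 (change −4). The coding error is gone, but the two visits then rest on different items.

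**The case against.** The SAP never says in words that 0 is summed. Item-level response scores could be read as the 1-to-5 codes alone, and the scoring paragraph cites two publications on the instrument that may say how 0 is handled. Those publications are not available here, so that cannot be checked. The sentence in the SAP is nevertheless explicit, carries no exception, and is what a programmer would implement.

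The case against is right on these points, each of which a reader might otherwise infer:

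- **That subjects who skip activities generally outscore subjects with no difficulty.** They do not. One zero with 14 items at code 2 gives 28, well above 15. The ordering is exact item by item, and for subjects with little or no difficulty on the rest.
- **That the domain scores are wrong as written.** They are unspecified. The −25 depends on an assumed linear recode that the SAP does not state.
- **That a 15-point shortfall is to be expected.** It is one scenario. Several items, such as adjusting to bright lights or bumping into objects, are hardly optional activities, so zeros may be few.
- **That the comparison between arms is biased.** Allocation is randomized and subjects are meant to be masked. The documents give no reason why skipping for non-visual reasons should differ by arm.

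**Conclusion.** The point holds for the total: read with the form it refers to, the stated rule turns a not-applicable answer into the best available score. This rests on taking the SAP sentence at its word, since no other section qualifies it. For the domains the finding is narrower: the position of code 0 on the 0–100 scale is not given.

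The error is one point per skipped item relative to no difficulty, and k × m points relative to a prorated total. The effect on arm means cannot be sized without the rate of 0 answers. The GQL-15 is untested and lies outside the fixed sequence in SAP 6.4, so the consequence is confined to the exploratory tables. It should be corrected before unmasking, but it does not threaten the trial's main conclusions.

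**What to change.** Amend SAP section 10 to state that:

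- code 0 is not applicable and is set to missing in the total and in every domain;
- the total is 15 × the mean of the items answered 1–5, provided a pre-specified minimum number is answered (for example, half), and is otherwise missing;
- responses 1–5 map to 0–100 by a stated formula, for example (response − 1) × 25;
- each domain is averaged over its answered items and is missing if none is answered, so outdoor mobility is missing when its one item is coded 0.

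Treating 0 as not applicable follows from the form itself. The threshold and the mapping are workable choices that the sponsor should check against the scoring publications it cites. A count of 0 answers by arm and visit would show how often the rule matters, and how far changes rest on different items at the two visits.

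The cost is SAP wording and a small programming change. No data collection changes.
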